8.4 Pregnancy Reporting

If a participant becomes pregnant during the study or within the Safety Follow-up Period defined in the protocol, the Investigator is to stop dosing with study drug(s) immediately and the participant

should be withdrawn from the study. Early study termination procedures should be implemented at that time.

If the female partner of a male participant becomes pregnant while the participant is receiving study drug or within the Safety Follow-up Period defined in the protocol, the Investigator should notify as described above.

The pregnancy should be followed until the outcome of the pregnancy, whenever possible. Once the outcome of the pregnancy is known, the EIU form should be completed and faxed/emailed to _______. If the outcome of the pregnancy meets the criteria for immediate classification as an SAE (i.e., postpartum complication, spontaneous abortion, stillbirth, neonatal death, or congenital anomaly), the Investigator should follow the procedures for reporting an SAE.

8.5 Expedited Reporting

The Sponsor/designee will report all relevant information about Suspected Unexpected Serious Adverse Reactions (SUSARs) that are fatal or life-threatening as soon as possible to the PMDA, Japan, and in any case no later than 7 days after knowledge by the Sponsor/designee of such a case. Relevant follow-up information will subsequently be communicated within an additional 7 days.

All other SUSARs will be reported to the PMDA as soon as possible but within a maximum of 15 days of first knowledge by the Sponsor/designee.

The Sponsor/designee will also report any additional expedited safety reports required in accordance with the timelines outlined in country-specific legislation.

The Sponsor/designee will also inform all Investigators as required per local regulation.

The requirements above refer to the requirements relating to investigational medicinal product.

[figure not shown]
8.6 Special Situation Reports

Special situation reports include reports of overdose, misuse, abuse, medication error, and reports of adverse reactions associated with product complaints.

- Overdose: Refers to the administration of a quantity of a medicinal product given per administration or cumulatively (accidentally or intentionally), which is above the maximum recommended dose according to the protocol. Clinical judgement should always be applied. In cases of a discrepancy in the drug accountability, overdose will be established only when it is clear that the participant has taken additional dose(s), or the Investigator has reason to suspect that the participant has taken additional dose(s).
- **Misuse:** Refers to situations where the medicinal product is intentionally and inappropriately used in a way that is not in accordance with the protocol instructions or local prescribing information and may be accompanied by harmful physical and/or psychological effects.

- **Abuse:** Is defined as persistent or sporadic, intentional excessive use of a medicinal product, which is accompanied by harmful physical or psychological effects.
- Medication error: Is any unintentional error in the prescribing, dispensing, or administration
 of a medicinal product by a healthcare professional, participant, or consumer, respectively. The
 administration or consumption of the unassigned treatment and administration of an expired
 product are always reportable as medication errors, cases of participants missing doses of
 investigational product are not considered reportable as medication error.
- Product complaint: Is defined as any written, electronic, or oral communication that alleges
 deficiencies related to the identity, quality, durability, reliability, safety, effectiveness, or
 performance of a drug or device after it is released for distribution. A special situations form
 will only be completed if a complaint is associated with an adverse drug reaction.

All special situation events as described above must be reported on the Special Situations Report form and faxed/emailed to (contact information listed below) within 24 hours of knowledge of the event. All AEs associated with these Special Situation reports should be reported as AEs or SAEs as well as recorded on the AE eCRF and/or the SAE report form. Details of the symptoms and signs, clinical management, and outcome should be provided, when available.

8.7 Clinical Laboratory Evaluations

Blood for chemistry and hematology will be obtained as indicated in Appendix A and sent to a central laboratory for analysis. See Appendix B for a complete list of analytes. Blood samples for chemistry and hematology must be obtained under fasting conditions (i.e., after the participant has fasted for approximately 8 hours). For the purposes of this study, fasting will be defined as nothing by mouth except water and any essential medications. If a participant is not fasting, the Investigator should reschedule the visit as soon as possible. Estimated glomerular filtration rate will be calculated using the Chronic Kidney Disease Epidemiology Collaboration equation.⁶ At the Screening Visit only, the chemistry panel will include HbA1c.

A urine pregnancy test will be performed for women of childbearing potential at the Screening Visit (Visit 1) prior to their participation in the study and at the Safety Follow-Up Visit (Visit 6), and the Early Termination Visit, if appropriate.

An FSH test will be performed at the Screening Visit prior to participation in the study in women <55 years of age for whom it has been ≥1 year since their last menstrual period to confirm a postmenopausal state.

Blood samples for PK assessment will be collected as indicated in Appendix A. On Day 1 (Visit 2), a PK sample will be collected pre-dose. The subsequent post-dose PK samples should be collected once at approximately the same time at each visit.

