8.1.4 Events of Special Interest

Events of special interest (ESIs) will be monitored over time, regardless of whether these events were reported as AEs. Any events that qualify as an AE or SAE will be reported accordingly (see Sections 8.1, 8.2, and 8.3).

ESIs will include hepatic abnormalities, muscle-related abnormalities, new-onset diabetes mellitus (NODM) and/or hyperglycemia, renal abnormalities, and ophthalmic events (i.e., macular degeneration), described as follows:

- AST or ALT >3 × ULN;
- Bilirubin >2 × ULN;
- CK >5 × ULN;
- NODM or worsening of glycemic control;

Note: NODM is defined by 1 or more of the following criteria, based upon information from AE, medication, and laboratory data:

- o AE indicating new type 1 or type 2 diabetes;
- o Initiation of anti-diabetes medication with confirmation of the diagnosis of diabetes;
- HbA1c \geq 6.5% (48 mmol/mol); and/or
- o Two consecutive values of fasting plasma glucose that are ≥ 126 mg/dL (7.0 mmol/L).

Note: Worsening of glycemic control will be defined as an HbA1c increase from Baseline >0.5% and/or a new concomitant medication or increase in current antidiabetic therapy in a participant with a Baseline HbA1c $\ge 6.5\%$.

- Both eGFR <30 mL/min/1.73 m² AND a >25% decrease in eGFR from Baseline, calculated using the Chronic Kidney Disease Epidemiology Collaboration equation; and
- Macular degeneration.

These ESIs will be monitored through review of the AE and laboratory databases.

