9.2.2.1 Analysis of events of special interest

Liver-associated enzymes and total bilirubin will be summarized by the value and change from Baseline in the value, by treatment group and visit. In addition, the number and percent of participants with abnormal values for ALT, AST, and total bilirubin will be summarized. These summaries of participants with abnormal values will be performed overall; by normal Baseline; and by abnormal Baseline for ALT, AST, and total bilirubin individually. Hy's Law criteria ($>3 \times$ ULN for either ALT or AST, with accompanying total bilirubin $>2 \times$ ULN) will also be applied to the data. Any potential Hy's Law cases will be listed separately.

Muscle-related abnormalities will be summarized by treatment group. CK levels will be summarized by the value and change from Baseline in value, by treatment group and visit. In addition, the number and percent of participants with abnormal CK values will be summarized. These summaries of participants with abnormal CK values will be performed overall, by normal Baseline CK, and by abnormal Baseline CK.

Cases of NODM will be recorded and summarized using the appropriate system organ class. These events will be summarized by severity and relationship to study drug for each treatment group. Fasting plasma glucose and HbA1c will be monitored as specified in Appendix A.

Baseline eGFR will be summarized by treatment group for actual value and for Baseline eGFR categories. Shift tables of eGFR category from Baseline to End of Treatment (EOT) will be provided by treatment group. Shift tables of urine albumin-creatinine ratio and urine protein-creatinine ratio from Baseline to EOT will be provided by treatment group. Values of CK

from Baseline to EOT will be summarized by treatment group and by Baseline eGFR category. Muscle-related abnormalities will be summarized by treatment group and by Baseline eGFR category.

Cases of macular degeneration will be recorded and summarized using the appropriate system organ class. These events will be summarized by severity and relationship to study drug for each treatment group.

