APPENDIX B: CLINICAL LABORATORY ANALYTES

Standard Safety Chemistry Panel

Alanine aminotransferase Albumin
Alkaline phosphatase Amylase
Aspartate aminotransferase Bicarbonate
Blood urea nitrogen Calcium

Chloride Creatine kinase

Creatinine Estimated glomerular filtration rate [1]

Gamma-glutamyl transferase Glucose (fasting)

Glycosylated hemoglobin [2] High-sensitivity C-reactive protein

Inorganic phosphorus Lactate dehydrogenase

Lipase Potassium
Sodium Total bilirubin
Total protein Uric acid

- Calculated using the Chronic Kidney Disease Epidemiology Collaboration equation. (Source: CKD-EPI equations for glomerular filtration rate [GFR]. MDCalc. https://www.mdcalc.com/ckd-epi-equations-glomerular-filtration-rate-gfr. Accessed 19 November 2021.)
- Screening Visit only.

Endocrinology

Follicle-stimulating hormone [1]

 A follicle-stimulating hormone test will be performed in women <55 years of age for whom it has been ≥1 year since their last menstrual period.

Hematology

Hematocrit Hemoglobin

Platelets Red blood cell count

White blood cell count and differential [1]

 Manual microscopic review is performed only if white blood cell count and/or differential values are out of reference range.

Pregnancy Test

Urine [1]

1. For women of childbearing potential only.

Lipid Profile

Apolipoprotein B
High-density lipoprotein-ApoE [1]
Low-density lipoprotein cholesterol [2]
Triglycerides

Apolipoprotein E (ApoE) High-density lipoprotein cholesterol Non-high-density lipoprotein cholesterol Very low-density lipoprotein cholesterol

- 1. With and without apolipoprotein C3.
- 2. Calculated using the Friedewald equation unless triglycerides (TGs) ≥400 mg/dL or low-density lipoprotein cholesterol (LDL-C) ≤50 mg/dL. If TG ≥400 mg/dL or LDL-C ≤50 mg/dL, then LDL-C level will be measured directly by preparative ultracentrifugation, also referred to as beta quantification. (Source: LDL calculated. MDCalc. https://www.mdcalc.com/ldl-calculated. Accessed 19 November 2021.) In addition, for all participants, LDL-C will be measured by preparative ultracentrifugation, also referred to as beta quantification, at Baseline (Day 1; Visit 2) and at the end of the 8-week Treatment Period (Day 56; Visit 5).

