3.1.2 Analysis Visits

Scheduled visits will be assigned to analysis visits as recorded on the case report form (CRF). Early termination visits will be assigned to analysis visits according to the following visit windows:

Analysis Visit	Target Analysis Day	Low Analysis Day	High Analysis Day
Day 1	1	NA	NA
Week 2	14	2	21
Week 4	28	22	42
Week 8	56	43	70
Safety Follow-up	84	71	

Unscheduled visits recorded on the CRF will not be re-assigned and remain labeled as unscheduled.

3.1.3 *Definition of Baseline*

Unless otherwise stated, Baseline will be defined as the last measurement prior to the first dose of study drug.

3.1.4 *Summary Statistics*

Categorical data will generally be summarized with counts and percentages of participants. The denominator used for the percentage calculation will be clearly defined. Continuous data will generally be summarized with descriptive statistics including n (number of non-missing values), mean, median, standard deviation, minimum, and maximum.

3.1.5 *Evaluation of Site Effect*

This is a multi-center study. Sites will not be pooled for any planned inferential analysis but may be pooled for subgroup analysis to assess the heterogeneity of treatment effects among pooled sites. The final pooling algorithm, if needed, will be specified before treatment unblinding and will be provided as an addendum to the SAP. Additionally, a review of by-site effects will be performed in the context of data listing review.

3.1.6 *Handling of Dropouts and Missing Data*

Date Values

In cases of incomplete dates (e.g. adverse event (AE), concomitant medication, and medical history start and/or stop dates), the missing component(s) will be assumed as the most conservative value possible. For example, if the start date is incomplete, the first day of the month will be imputed for the missing day and January will be imputed for the missing month. If a stop date is incomplete, the last day of the month will be imputed for the missing day and December will be imputed for the missing month. Incomplete start and stop dates will be listed as collected without imputation.

Date imputation will only be used for computational purposes such as treatment-emergent status. Actual data values, as they appear in the original CRFs, will be presented within the data listings.

Non-Date Values

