3.7.6 Events of Special Interest

Liver-associated enzymes and total bilirubin will be summarized by the value and change from Baseline in the value, by treatment group and visit. In addition, the number and percent of participants with abnormal values for ALT, AST, and total bilirubin will be summarized. These summaries of participants with abnormal values will be performed overall; by normal Baseline; and by abnormal Baseline for ALT, AST, and total bilirubin individually. Hy's Law criteria ($>3 \times$ ULN for either ALT or AST, with accompanying total bilirubin $>2 \times$ ULN) will also be applied to the data. Any potential Hy's Law cases will be listed separately.

Muscle-related abnormalities will be summarized by treatment group. CK levels will be summarized by the value and change from Baseline in value, by treatment group and visit. In addition, the number and percent of participants with abnormal CK values will be summarized. These summaries of participants with abnormal CK values will be performed overall, by normal Baseline CK, and by abnormal Baseline CK.

Cases of NODM will be recorded and summarized using the appropriate system organ class. These events will be summarized by severity and relationship to study drug for each treatment group. Fasting plasma glucose and HbA1c will be monitored as specified in Appendix A (Schedule of Procedures) of the study protocol.

Baseline eGFR will be summarized by treatment group for actual value and for Baseline eGFR categories. Shift tables of eGFR category from Baseline to End of Treatment (EOT) will be provided by treatment group. Shift tables of urine albumin-creatinine ratio and urine protein creatinine ratio from Baseline to EOT will be provided by treatment group. Values of CK from Baseline to EOT will be summarized by treatment group and by Baseline eGFR category. Muscle related abnormalities will be summarized by treatment group and by Baseline eGFR category.

Cases of macular degeneration will be recorded and summarized using the appropriate system organ class. These events will be summarized by severity and relationship to study drug for each treatment group.

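### HbA1c is measured only at Screening, so two glycaemic special-interest criteria have no on-treatment data, and two promised urine-ratio shift tables have no data at all

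*Protocol*

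**What the plan says.** **Definitions.** Protocol 8.1.4 lists new-onset diabetes (NODM) and worsening of glycaemic control as events of special interest. For the first, "NODM is defined by 1 or more of the following criteria, based upon information from AE, medication, and laboratory data". There are four criteria: an adverse event of diabetes, starting anti-diabetes medication with a confirmed diagnosis, HbA1c of at least 6.5%, and two consecutive fasting glucose values of at least 126 mg/dL. For the second, "Worsening of glycemic control will be defined as an HbA1c increase from Baseline >0.5" (in percent), and/or a new or increased antidiabetic treatment where Baseline HbA1c is at least 6.5%. On detection: "These ESIs will be monitored through review of the AE and laboratory databases".

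**Monitoring.** Protocol 9.2.2.1 states "Fasting plasma glucose and HbA1c will be monitored as specified in Appendix A". SAP 3.7.6 repeats it: "Fasting plasma glucose and HbA1c will be monitored as specified in Appendix A (Schedule of Procedures) of the study protocol".

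**Collection.** Protocol 8.7 states "At the Screening Visit only, the chemistry panel will include HbA1c". Note j to Protocol Appendix A and SAP 3.7.2 say the same. Both Appendix B lists footnote HbA1c "Screening Visit only". Under SAP 3.1.3, "Baseline will be defined as the last measurement prior to the first dose of study drug".

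**Urine.** Protocol 9.2.2.1 and SAP 3.7.6 both commit to shift tables, Baseline to end of treatment, for the urine albumin-creatinine and protein-creatinine ratios. Protocol 8.7 and SAP 3.7.2 describe their Appendix B as the complete analyte list. The only urine item in either is the pregnancy test.

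**The concern.** A rule defined by change from Baseline needs a second measurement, and the schedule provides none. A shift table needs a value at each end, and for the urine ratios the schedule provides neither.

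Safety and tolerability is a stated secondary objective (Protocol 2.2). An empty table, or a count of zero where nothing was measured, can be read as absence of a signal. An HbA1c measured locally outside the schedule could still arise, but ascertainment would then be ad hoc and might differ between arms.

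**Working it through.** No sample-size or alpha figure is involved. The check sets what the analysis needs beside what is collected.

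**1. HbA1c time points.** Appendix A schedules fasting chemistry at Screening, Visits 2, 3, 4, 5 and 6, and Early Termination: 7 in all. Those after baseline are Visits 3, 4, 5, 6 and Early Termination: 5. Note j restricts HbA1c to Screening.

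- All chemistry time points: 1 of 7 has HbA1c.
- Post-baseline: 0 of 5.
- For a completer, who has no Early Termination visit: 1 of 6 overall and 0 of 4 post-baseline.

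**2. What each criterion needs.** Medication criteria are counted once per definition.

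| Criterion (Protocol 8.1.4) | Needs | Scheduled input |
|---|---|---|
| NODM: adverse event | AE data | Yes |
| NODM: medication | Medication data | Yes |
| NODM: HbA1c at least 6.5% | An on-study HbA1c | None; only the pre-treatment value |
| NODM: two fasting glucose values | Consecutive chemistry visits | Yes: 4 post-baseline values in a completer (Visits 3–6) |
| Worsening: HbA1c rise above 0.5% | 2 HbA1c values | 1 value, which is the Baseline |
| Worsening: medication | Medication data, Baseline HbA1c | Yes |

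Criteria that use an HbA1c result as the event: 1 of 4 for NODM plus 1 of 2 for worsening, so 2 of 6. Neither has scheduled post-baseline data. The Screening value is the last before first dose, so it is itself the Baseline and no difference can be formed. As written, worsening is left with its medication criterion; NODM keeps three of four.

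**3. Urine ratios.** Urine of any kind is scheduled at 3 time points (Screening, Visit 6, Early Termination), as a pregnancy test in women of childbearing potential only. None is scheduled at Visit 2 (Day 1) or Visit 5 (Day 56). The one other urine test named is the dipstick in the work-up of symptomatic creatine kinase elevation (Protocol 8.1.4.2), done only if indicated and yielding neither ratio. Each ratio is therefore collected at 0 of 7 time points, and 2 of 2 tables have no input. SAP section 5 lists two changes from the protocol and withdraws neither table.

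**4. A related gap.** Protocol 4.2 excludes Screening HbA1c of 10% or more, so a participant can enter with 6.5% to below 10% and already meet the NODM threshold. The HbA1c and glucose criteria carry no condition on timing or on diabetes at baseline. The planned NODM summary, by system organ class, severity and relationship, reads as AE-based; treatment-emergent events start after first dose (SAP 3.7.1) and pre-existing conditions are medical history (Protocol 8.1). The gap therefore matters only if cases are also counted from laboratory data, which the reference in 8.1.4 to the laboratory database suggests.

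**The case against.** The facts about collection are not in dispute. The case against concerns their weight.

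- **There is an adverse-event route.** Protocol 8.1 requires a worsening pre-existing condition to be reported as an AE, and SAP 3.7.1 has special-interest events flagged on the CRF and tabulated. A clinically recognised deterioration could therefore be reported. This stands, but it adds no AE criterion to the written definition of worsening, and 8.1.4 says special-interest events are followed whether or not reported as AEs.
- **No table of worsening is promised.** Correct. Only the two urine tables fail as named outputs; the HbA1c failure is of a stated rule.
- **A Screening value would never be read as new onset.** That is the sensible reading, and Protocol 8.1.4.3 speaks of diagnosis during the study. It leaves the HbA1c criterion with no scheduled data, so the conclusion is unchanged.
- **Safety data are used as available** (SAP 3.1.6), and SAP 3.7.2 mentions urine samples. The first covers missing values of collected variables. The second refers to the same schedule and to an analyte list whose only urine test is for pregnancy. Neither supplies the missing data.
- **Adding HbA1c touches clinical guidance.** A new on-study value could meet the 8.1.4 definition, to which the referral guidance in 8.1.4.3 points. This is a fair caution: the sponsor must reconcile those passages if it chooses collection.
- **The output is only descriptive.** True, and it limits the importance of the point.

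**Conclusion.** The concern holds. From scheduled data, the HbA1c rise cannot be computed and the 6.5% criterion has no on-study input: 2 of 6 criteria, with 0 of 5 post-baseline HbA1c measurements. Both urine-ratio shift tables have no input at any of 7 time points. The remaining AE, medication, fasting-glucose and eGFR outputs can be produced, and no efficacy result is affected. The lack of a baseline-diabetes condition is secondary and depends on whether a laboratory-based count is intended. The conclusion assumes that the schedule and analyte lists are complete as printed and that no unscheduled HbA1c or urine-ratio programme exists outside these documents. It should be corrected, but it does not threaten the trial's main conclusions.

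**What to change.** Reconcile Protocol 8.1.4, 8.7, 9.2.2.1 and Appendices A and B with SAP 3.7.2, 3.7.6 and Appendix B. Only data collection and analysis need change.

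- **HbA1c, one of two options.** (i) By amendment, add an HbA1c assay to the draws already scheduled at Visit 5 and Early Termination. At one per participant this is about 4 × 27 = 108 assays, with no extra visit or draw. (ii) Remove the two HbA1c criteria from the special-interest analysis, and state that NODM rests on AE, medication and fasting-glucose data and that worsening rests on medication data alone. This is wording only.
- **Urine ratios.** Delete the two shift tables (wording only). Unlike HbA1c, they have no suitable scheduled sample to use, since no urine is taken at Visit 2 or Visit 5.
- **NODM count.** If cases are to be counted from laboratory values, specify in the SAP that qualifying values are post-baseline and that participants with diabetes at baseline are not counted, identifying them from medical history, medication, Screening HbA1c and pre-dose glucose. If not, say that the summary is AE-based. Wording only.
- **Record.** List the changes in SAP section 5. How the referral guidance in Protocol 8.1.4.3 should relate to any revised definition is for the sponsor to reconcile.
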